4.1 Investigational Product

An investigational product, also known as investigational medicinal product in some regions, is defined a pharmaceutical form of an active substance or placebo being tested or used as a reference in a clinical study, including products already with a marketing authorization but used or assembled (formulated or packaged) differently than the authorized form, or used for an unauthorized indication, or when used to gain further information about the authorized form.

The investigational product should be stored in a secure area according to local regulations. It is the responsibility of the investigator to ensure that investigational product is only dispensed to study subjects. The investigational product must be dispensed only from official study sites by authorized personnel according to local regulations.

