4.5 Selection and Timing of Dose for Each Subject

Study drug may be administered in the clinical facility or self-administered by the subject or their caregiver at home. Caregivers will need to be properly instructed about study medication dosing requirements by the study staff. The same caregiver should assist the subject with their daily dosing.

Double blind study medication (BMS-986141 or matching placebo) will be taken once daily. The first dose of study medication should be taken as soon as possible after randomization. Subsequent doses including on Day 2 of the study should be taken in the morning and before breakfast. The subject must be in a fasted state for at least two (2) hours when taking study medication. Subjects should wait at least one (1) hour before consuming food.

Initially, each daily dose of double blind study medication will consist of 4 tablets. The double blind treatment period will be 28 days for Part 1 of the study and 90 days for Part 2 of the study. Drug supplies that may become available in early 2017 may allow for dosing with 2 tablets per day. Sites will be provided with instructions and guidance on how to implement this change if it is to occur.

Subjects treated in Part 1 of the study MUST be instructed to stop study medication dosing on Day 28, even if visit will not occur on exactly Day 28.

Sparse PK sampling will occur at the Day 28 visit. Subjects will be instructed not to take their study medication dosage on Day 28 prior to coming to the study site.

Additional drug, dosage and mode of administration

All subjects will be dispensed open label ASA at a dose prescribed by the investigator (not less than 75 mg and not to exceed 162 mg per day). It is recommended subjects remain on the same dose of ASA throughout the treatment period.

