8.2 Populations for Analyses

- The Enrolled Subjects Data Set will consist of all subjects who sign informed consent.
- The Randomized Subjects Data Set will consist of all randomized subjects regardless of whether they received treatment. This is also known as the Intent to Treat (ITT) population. This will be the primary efficacy data set. Data in this data set will be analyzed based on randomized treatment group.
- The Treated Subjects Data Set will consist of all subjects who receive at least one dose of study medication during the treatment period. This will be the primary safety data set. Data in this data set will be analyzed based on randomized treatment, except in the following cases:
 - If a subject received the same incorrect treatment throughout the study (until either Day 28 or Day 90, or until discontinuation of the study drug), then the subject will be analyzed based on the treatment received.
 - If a subject received study drug from more than one treatment group, and none of the administrations were consistent with the assigned randomized treatment group, then the subject will be analyzed based on the first treatment received.

- The Pharmacodynamic analysis dataset will consist of subjects in the Randomized Subject Dataset who have at least one pharmacodynamic endpoint assessed.
- The Pharmacokinetic analysis dataset will consist of all subjects who receive BMS-986141 and have at least one post dose PK sample. Additionally, the evaluable PK population is defined as subjects who have adequate PK profiles on Day 1.

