6.3 Populations for Analyses

The analyses will use several populations as defined below.

- 1) All Enrolled Subjects: Includes all subjects who signed informed consent.
- 2) All Randomized Subjects / Intent to Treat (ITT) Population: Includes all subjects who were randomized to a treatment, regardless of whether they received study drug or not. This population will be analyzed according to the treatment assigned at randomization.
- 3) All Evaluable Subjects: Includes All Randomized Subjects as above, excluding those subjects' visits where relevant protocol deviations occurred, as defined in [Section 7.2.2](#).
- 4) All Treated Subjects: Includes all subjects who received at least one dose of study medication. This will be the primary population used in safety analyses and will be analyzed according to the treatment assigned at randomization, except in the following cases:
 - If a subject received the same incorrect treatment throughout the study (until either Day 28 or Day 90, or until discontinuation of the study drug), then the subject will be analyzed based on the treatment received.

- If a subject received study drug from more than one treatment group, and none of the administrations were consistent with the assigned randomized treatment group, then the subject will be analyzed based on the first treatment received.
- 5) Pharmacodynamics (PD) Population: A subset of the ITT Population that includes subjects with at least one pharmacodynamic endpoint assessed following the first dose of BMS-986141.
 - 6) Pharmacokinetic (PK) Population: Includes all subjects treated with BMS-986141 who also have at least one post-dose PK sample. The Evaluable PK Population is further defined as a subset of the PK Population including subjects who have adequate PK profiles on Day 1.

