7.1 General Methods

Descriptive summaries will be presented for continuous variables using number of subjects (N), mean, standard deviation (SD), median, minimum and maximum. Geometric mean and coefficient of variation (%CV) will also be presented for sample plasma concentration-time data and PK parameters. Descriptive summaries for categorical variables will utilize counts and percentages.

Adverse events will be coded according to the most recent Medical Dictionary for Regulatory Activities (MedDRA) version. Adverse events will be summarized according to the MedDRA coded Preferred Terms (PT) by System Organ Class (SOC). Previous and concomitant medications will be coded using the WHO Drug Dictionary version.

Unless otherwise specified, baseline is defined as the last non-missing result with a collection date-time prior to the date-time of the first active dose of study medication.

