7.5.2 Secondary Efficacy Analyses

The same approach used in the primary analysis will be repeated on the secondary endpoints.

- The incidence of major adverse cardiovascular events (MACE) by Day 90, defined as a composite of adjudicated recurrent stroke, myocardial infarction, or CV death
- The incidence of a composite of adjudicated recurrent ischemic stroke, myocardial infarction, or CV death by Day 90
- The incidence of adjudicated symptomatic recurrent stroke (including fatal and non-fatal) by Day 28
- The incidence of the composite of unrecognized brain infarction assessed by MRI at Day 28 and MACE by Day 90

In addition, a sequential testing procedure will be used for the primary and MACE endpoints as described below.

- 1) If a dose-response relationship is established for the primary endpoint at the one-sided 0.15 level, then the primary analysis will be repeated at a one-sided alpha level of 0.025.
- 2) If this analysis at the one-sided 0.025 level also demonstrates a dose-response relationship, then the dose-response relationship for the MACE endpoint will be tested using a one-sided alpha level of 0.025.

Each of these sequential testing analyses will be performed. Their interpretation will be guided by the sequential testing procedure.

7.5.3 *Other Efficacy Analyses*

The primary analysis will be repeated for the composite endpoint of recurrent ischemic stroke or any adjudicated arterial thrombotic events up to 90 days. As well, the primary analysis will be repeated using each of its components, individually, as the response variable.

Additionally, the following exploratory analyses may be explored:

- [REDACTED]

7.6 *Safety Analyses*

Analysis of all safety data will be conducted on all treated subjects and will follow the BMS guideline of analysis of safety data⁹. Safety will be summarized for each parameter by treatment group, as well as for all subjects receiving BMS-986141. Summaries of the frequency of subjects experiencing certain events, such as adverse events, elevated labs or vital signs, or elevated ECGs, will be summarized by treatment and study time period (1A, 2A, 2B), and for study part 2.

The evaluation of safety is based on adjudicated bleeding events, clinical adverse events (AEs), vital signs, ECG results, and clinical laboratory results.

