8 CONVENTIONS

Standard time windowing, imputation rules, and counting rules will be applied according to the GBS Requirements for Statistical Outputs¹⁰. Unless otherwise defined, baseline is defined as the last non-missing value prior to the first dose of study drug.

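### Read literally, the SAP's PD population leaves out the placebo arm, and the SAP's two default baselines conflict

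*SAP*

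**What the plan says.** **PD population.** Protocol 8.2 defines the PD dataset as "subjects in the Randomized Subject Dataset who have at least one pharmacodynamic endpoint assessed", with no condition on which drug was taken. SAP 6.3, item 5, takes a subset of the ITT population and requires "at least one pharmacodynamic endpoint assessed following the first dose of BMS-986141". Protocol 3.1 describes a platelet-aggregation sub-study of about 50 subjects in each arm. Protocol 8.4.5 plans summaries of each biomarker and its change from baseline, split by treatment and time point. The corresponding SAP section, 7.8, is redacted.

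**Baseline.** SAP 7.1 takes the last non-missing result "prior to the date-time of the first active dose of study medication". SAP section 8 says "baseline is defined as the last non-missing value prior to the first dose of study drug". Each is offered as the general default unless something else is stated, and neither is given precedence. The SAP does not define an active dose.

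**What counts as study drug.** Protocol 4.5 states: "Double blind study medication (BMS-986141 or matching placebo) will be taken once daily". Protocol 4.1 defines investigational product as "a pharmaceutical form of an active substance or placebo being tested or used as a reference in a clinical study", so placebo is included. Protocol section 4 also counts open-label ASA as study drug, and Protocol 4.7 includes ASA when it speaks of study medication.

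**The concern.** The sub-study is placebo-controlled, and all subjects take ASA after a recent stroke or TIA. Without placebo subjects in the PD set, a change in platelet aggregation on BMS-986141 could not be separated from the effect of ASA or of time since the event. A programmer who followed SAP 6.3 as written would produce PD tables with no placebo column.

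The baseline rule feeds the by-treatment change summaries for laboratory tests, ECG and vital signs (SAP 7.6.5 to 7.6.7). It also feeds the out-of-range vital-sign criteria in Table 7.6.7-1, each of which requires a change from baseline. Those outputs need one rule that works the same way in every arm. Two unranked defaults leave the choice to be made at programming.

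**Working it through.** This is a point about definitions. The documents give no sample-size or power figure for the PD or change-from-baseline summaries, so there is no stated figure to reproduce. The check is a comparison of the texts followed by a count.

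**Step 1: who qualifies for the PD set.**

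| Source | Condition | Placebo subject with a PD sample |
|---|---|---|
| Protocol 8.2 | Randomized, at least one PD endpoint | Included |
| SAP 6.3, item 5 | ITT, PD endpoint after first BMS-986141 dose | Excluded: no such dose exists |

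**Step 2: is BMS-986141 used as shorthand for blinded medication?** Other SAP text suggests not. The PK population, the next item in 6.3, is limited to subjects treated with BMS-986141, and Protocol 5.5.1 says that placebo PK samples are not analysed. SAP 7.6 presents safety by treatment group "as well as for all subjects receiving BMS-986141", so there the drug name marks the pooled active group. The All Treated population, which must include placebo, is defined by study medication and not by the drug name.

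**Step 3: size.** Input: about 50 per arm (Protocol 3.1). Assumption: all four arms take part.

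- Sub-study total: 4 × 50 = 200
- PD set under Protocol 8.2: about 200, of whom about 50 are placebo
- PD set under the literal SAP wording: 200 − 50 = 150, of whom 0 are placebo
- Share excluded: 50 / 200 = 25%
- If only three arms took part (8 mg never opened): 3 × 50 = 150, and 50 / 150 = 33%

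**Step 4: the two baselines.**

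| Source | Anchor | Placebo subject |
|---|---|---|
| SAP 7.1 | First active dose | No anchor date, if active means BMS-986141 |
| SAP 8 | First dose of study drug | Has a baseline, since placebo is study drug |

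**Step 5: would copying SAP 8 into 7.1 be enough?** No. Protocol 3.1 starts ASA at a time set by local standard of care, which may be before the first blinded dose. Because the protocol's terms for study drug and study medication include ASA, either term alone could be read as placing baseline before the first ASA dose.

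**The case against.** The best reply is that this is loose drafting and the intent is clear. The sub-study recruits in every arm, and Protocol 8.4.5 plans biomarker summaries by treatment, so placebo PD data are collected in order to be reported. SAP 7.8 may name a population and baseline that resolve the matter. The visible PD plan is descriptive and exploratory. On baseline, SAP 7.1 is only a default, an active dose could mean a dose in the blinded treatment period, SAP 8.3 counts visits from the start of study medication, and the marked-abnormality appendices compare with pre-dose values without distinguishing arms.

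Most of this stands, and it rules out two stronger readings that a reader might infer.

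- **That all 348 planned placebo subjects have no baseline, so placebo disappears from the change-from-baseline summaries.** This follows only if SAP section 8 is ignored and active is read in one way. Under section 8 no placebo subject lacks a baseline for this reason, and SAP 7.6 plans safety summaries by treatment in all treated subjects. The 348 is also a randomization target (SAP Table 5-1), not a count of treated subjects.
- **That the PD analysis will in fact be run without placebo.** With SAP 7.8 redacted, the documents cannot show this.

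The reply does not remove the defect in SAP 6.3. Clear intent elsewhere makes the sentence wrong; it does not make it consistent. The departure from Protocol 8.2 is not explained in the visible text, although SAP 7.2.2 says that changes from protocol-specified analyses will be defined in the SAP.

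**Conclusion.** The point holds in a limited form. The PD population rule in SAP 6.3 contradicts Protocol 8.2 and, applied as written, removes the entire placebo arm: 25% of the sub-study with four arms, 33% with three. These shares rest on the protocol's approximate figure of 50 per arm and on a literal reading of the SAP sentence.

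Separately, SAP 7.1 and SAP 8 are conflicting default baselines, of which only the first fails for placebo. That is an inconsistency to settle, with no demonstrated loss of data.

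The matter is minor. The primary and secondary efficacy endpoints are incidences analysed in the ITT population (SAP 4.1, 4.2 and 7.5), so neither definition touches them, and no sample size, power or alpha figure changes. It is still worth settling before unblinding, so that neither the PD population nor the baseline has to be chosen with treatment codes in hand.

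**What to change.** Use one anchor in three places: the first dose of double-blind study medication, whether BMS-986141 or its matching placebo.

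- **SAP 6.3, item 5:** replace the reference to the first BMS-986141 dose with this anchor. The SAP's requirement for a post-dose PD assessment can stay.
- **SAP 7.1:** replace the reference to the first active dose with the same anchor. Deleting the word active is not enough, because study medication can include ASA.
- **SAP 8:** replace the reference to study drug with the same anchor, or delete the sentence and refer to 7.1.

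Then check that SAP 7.8 uses the corrected population and baseline. The cost is three wording edits in the SAP, with no new data and no change to trial conduct.

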7 STATISTICAL ANALYSES

SAS® version 9 or higher will be used for statistical analyses, tabulations and graphical presentations. The DoseFinding package for R (version 3.1.3 or higher) will also be used in the conduct of the multiple comparisons modelling analyses.

7.1 General Methods

Descriptive summaries will be presented for continuous variables using number of subjects (N), mean, standard deviation (SD), median, minimum and maximum. Geometric mean and coefficient of variation (%CV) will also be presented for sample plasma concentration-time data and PK parameters. Descriptive summaries for categorical variables will utilize counts and percentages.

Adverse events will be coded according to the most recent Medical Dictionary for Regulatory Activities (MedDRA) version. Adverse events will be summarized according to the MedDRA coded Preferred Terms (PT) by System Organ Class (SOC). Previous and concomitant medications will be coded using the WHO Drug Dictionary version.

Unless otherwise specified, baseline is defined as the last non-missing result with a collection date-time prior to the date-time of the first active dose of study medication.

7.1.1 General Methods for Study Periods

Given the different planned study treatment durations between Part 1 (treatment duration of 28 days) and Part 2 (treatment duration 90 days) and time at which randomization will be extended to include the high dose of BMS-986141 (8 mg) following review of safety data by the DMC, select summaries will be tabulated by the following three applicable study time periods with respect to study part and study phase:

- Part 1, Phase A (1A)
- Part 2, Phase A (2A)
- Part 2, Phase B (2B)

Summaries will also be tabulated for Part 2 overall, to include data from all subjects with a planned treatment duration of 90 days. The following summaries will be tabulated as indicated above.

- Demographics
- Baseline characteristics
- Relevant protocol deviations
- Disposition
- Concomitant medications, including CYP3A4 inhibitor use
- Study drug exposure and compliance
- Bleeding events
- Adverse events, including overall AEs, SAEs, AEs leading to discontinuation, related AEs, and deaths
- Abnormal laboratory results, including renal biomarkers
- Abnormal ECG results
- Out of range vital signs

7.1.2 General Methods for Efficacy Analyses

Generalized Multiple Comparison Modelling (gMCP-Mod)

To demonstrate the dose-response relationship between BMS-986141 treatment (including placebo) and the primary endpoint, the primary analysis will be based on a generalized Multiple Comparisons and Modeling (gMCP-Mod) analysis⁵⁶. This analysis tests for a dose-response relationship, allowing for uncertainty in the dose-response relationship through inclusion of contrasts from multiple pre-specified candidate models to assess dose-response. If a dose-response relationship exists, then fitted estimates for the incidence of the primary endpoint will be calculated in each of the treatment groups using the selected dose-response models.

The gMCP-Mod procedure extends the MCP-Mod methodology to non-continuous endpoints. This is accomplished by decoupling the dose-response model from the expected response through the use of an ANOVA style parameterization of the dose-response parameter. For the binary endpoint used in this study, a logistic regression of the event proportion at each dose level will be used, following adjustment for study time period (1A, 2A, 2B) via the inclusion of an additive covariate. After this first step, the mean parameter estimates from the logistic model and the corresponding covariance matrix, both of which are on the logit scale, will then be used during the rest of the gMCP-Mod procedure. Point estimates from the selected models will be displayed on the proportion scale in all statistical outputs.

Candidate Models and Multiple Testing Procedure

There are two candidate models that will be considered for the primary analysis. These are an Emax model and a logistic model, where dose-response will be tested using dose levels of 0 (placebo), 1, 2, and 2.3 (corresponding to 0.8 mg, 4.8 mg, and 8 mg)⁷.

The MCP-Mod procedure requires certain parameter estimates be pre-specified for the candidate models based on available information in order to derive optimum contrast coefficients for testing the null hypothesis: that a dose-response does not exist in any of the candidate models. It

is through testing this hypothesis that the model which best describes the dose-response relationship will be identified⁸. The parameters used to determine the contrast for testing will assume a placebo event rate of 14% and maximum risk reduction of 4.2%. For the Emax model, the required parameter estimates used will be 1.0 for the dose corresponding to half of the maximum effect and 1.0 for a “Hill” parameter that determines the steepness of the model at the dose of half effect. For the logistic model, these parameter estimates used will be 1.0 for the dose corresponding to half effect and 0.1 for the parameter that determines the steepness of the curve. These pre-specified parameter estimates will remain fixed through the contrast testing portion of the gMCP-Mod procedure in order to preserve the type I error.

The gMCP-Mod procedure for non-continuous endpoints diverges from the original MCP-Mod procedure in the calculation of the optimum contrast coefficients. The gMCP-Mod methods that will be used to calculate the optimum contrast coefficients require the pre-specified model parameters from above along with the covariance matrix from the logistic regression in the first step. In practice, since the covariance matrix in the first step is based on actual data, the optimum contrast coefficients are recalculated when the actual data become available. The parameter estimates for the candidate models, however, will remain fixed.

These optimal contrast coefficients follow the form given below, and will be recalculated as described using the DoseFinding package in R once the actual data are available.

$$c_m^{opt} \propto S^{-1} \left(\mu_m - \frac{\mu_m' S^{-1} \mathbf{1}}{\mathbf{1}' S^{-1} \mathbf{1}} \right)$$

Where μ_m is the event rate on the logit scale based on the corresponding candidate model m ($m=1, 2$) at the specified dose levels, and S corresponds to the covariance matrix from the logistic regression on the actual data in the first step.

In order to demonstrate a dose-response relationship, the following global hypothesis will be tested:

$$H_0: c_m^{opt} \mu \geq 0 \text{ for all } m \in \{1, 2\}$$

$$H_1: c_m^{opt} \mu < 0 \text{ for at least one } m \in \{1, 2\}$$

where μ is the true event rate on the logit scale at the specified dose levels.

For each candidate model ($m=1, 2$), the contrast test statistic (z_m) is calculated as standardized linear combinations of the estimated event rate on the logit scale from the logistic regression using the optimal contrast coefficients associated with that candidate model.

A multiplicity-adjusted critical value will be determined from the joint multivariate normal distribution of the contrast test statistics at the overall one-sided alpha level of 0.15. If either test statistic that exceeds this critical value, a dose-response relationship will be demonstrated.

Modelling and Estimation

The model for estimation will be selected from among the two candidate models with a contrast test statistic that is greater than or equal to the multiplicity-adjusted critical value. If both

candidate models have such contrast test statistics, then both models will be employed using a weighted averaging technique based on their relative Bayesian Information Criteria (BIC), for the purposes of estimation. If neither candidate model has a contrast test statistic that is greater than or equal to the multiplicity-adjusted critical value, then the analysis will end, indicating that a dose-response relationship cannot be established.

In this manner, the point estimates for the means will be generated from the selected model as described in the efficacy analyses in [Section 7.5](#).

